The intensive PK sampling for LQT-1213 will be conducted on Days 2 and 4, and the morning of Day 5. Continuous 12-lead 24-hour Holter data will be collected on Days –1 through 5, as detailed in the PK and PD time points table (Section 8.4 Appendix D). All Holter data starting on Day -1 will be stored for potential future analysis. On each day, the Holter data card will be removed and a new one inserted approximately 90 minutes before first dosing on each Days and on Day 5. ECG extraction time points for potential future analysis are detailed in the PK and PD time points table (Section 8.4, Appendix D).

Serum potassium and magnesium will be checked daily while participants are housed (Days –1, 1, 2, 3, 4, and 5) and may be repeated at any time at the investigator's discretion. Potassium <3.8 mg/dL and magnesium <1.8 mg/dL will result in additional electrolyte supplementation. Electrolyte supplementation can be administered 12-18 hours after the morning dose of LQT-1213.

Safety assessments will include AEs, clinical laboratory test results, vital signs measurements, continuous telemetry ECG monitoring, and safety 12 lead ECG findings. Bedside safety 12-lead ECGs will be collected by the CRU staff and reviewed by the investigator. The safety ECG data, including all time points, will be recorded on the electronic case report form, and be used for evaluating general safety of the participants with LQT2 or LQT3 during the study and for evaluation of an AE.

The dosing, meal timing, and PK and ECG time points and extractions may be modified based on emerging data.

Figure 5-2 Study Schematic - Part 2

Abbreviations: TID, 3 times a day; CRU, clinical research unit; EOS, end of study; EOT, end of treatment; ET, early termination; F/U, Follow-Up; QTcF, QT interval corrected for heart rate by Fridericia's formula.

- a Up to 12 participants with LQT2 and up to 12 participants with LQT3 will be enrolled, of which the first 2 participants for each LQT subtype require having an implantable cardioverter defibrillator (ICD), which must have had ICD implantation at least 2 months before Screening. All participants with LQT2 or LQT3 will have a OTcF ≥480 and ≤560 ms.
- b On Day 1, participants with LQT2 or LQT3 will undergo baseline 24-hour 12-lead high fidelity Holter monitoring during placebo single-blind administration.
- c LQT-1213: LQT-1213 will be administered TID (at time 0, 8, and 16 hours) on Day 2 and 3, with the final dose on Day 4 at time 0, though these time points may be adjusted based upon emerging data.
- d Approximately 7 days after discharge from the CRU, the Follow-up Visit will be conducted remotely via telephone call.

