- 10. Abnormal renal function with an estimated glomerular filtration rate (eGFR) of <70 mL/min/1.73 m², with eGFR calculated by the Chronic Kidney Disease Epidemiology Collaboration [CKD-EPI] formula at Screening. One retest of the exclusionary eGFR value is allowed at the discretion of the investigator.
- 11. Subject has abnormal liver function tests (transaminases or total bilirubin) greater than 2.5 × the upper limit of normal at Screening or baseline. One retest of exclusionary abnormal liver function tests is allowed at the discretion of the investigator.
- 12. Subject has a positive serology test for HIV antibodies, hepatitis B surface antigen, or hepatitis C virus antibody at Screening.
- 13. Subject has a hemoglobin <11.0 g/dL, potassium <3.8 mg/dL, magnesium <1.9 mg/dL, or calcium <8.5 mg/dL at Screening or baseline. One retest of exclusionary hemoglobin, potassium, magnesium, and calcium is allowed at the discretion of the investigator. Electrolyte supplementation is allowed at any time as long as it is >4 hours before dosing.
- 14. Subject has a history of hypersensitivity to drugs with a clinically significant reaction or any clinically significant hypersensitivities.
- Subject has an allergy to band aids, adhesive dressing, or medical tape.
- 16. Subject has a history within the past 2 months of strenuous exercise (eg, marathon running) and is unwilling to refrain from strenuous exercise from 7 days before Check-in and until the end of the study. Subject has abnormal creatine phosphokinase test greater than 3 × the upper limit of normal at Screening and baseline. One retest of exclusionary abnormal creatine phosphokinase tests is allowed at the discretion of the investigator.
- 17. Subject is unable to refrain from or anticipates the use of any drug, including prescription and nonprescription medications (with the exception of hormonal contraception), herbal preparations, or vitamin supplements beginning 14 days before the first dose and until the end of the study. After dosing, acetaminophen (up to 2 g per

- 24 hours) may be administered at the discretion of the investigator or designee.
- a. Hepatic or renal clearance altering agents within 30 days before the first dose and until the end of the study.
- b. Avoid vaccinations from Screening until the end of the study.

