- 9. At Screening and on Day -1, if the triplicate 12-lead ECG demonstrates any of the following: mean PR >250 ms; QRS >110 ms, or QTcF >560 ms and <480 ms; bundle branch block or significant ST-T wave abnormalities or flat T waves that could interfere with QT analysis. Heart rate <45 bpm, unless receiving a beta-blocker in which case <40 bpm, or HR >95 bpm. If any of these exclusionary criteria are met, then a second set of triplicate ECGs may be acquired, and the mean values may be used. For participants on beta blockade, the PR interval may be higher than 250 ms with sponsor and investigator approval.
- 10. Atrial pacing rate set to \geq 80 bpm in those with atrial pacing.
- 11. Participant has a pacemaker or ICD that is actively used for ventricular pacing.
- 12. Known sensitivity to kinase inhibitors or clinically significant drug allergies to any of the components of LQT-1213.
- 13. Abnormal renal function with an eGFR of <60 mL/min/1.73 m², with eGFR calculated by the CKD-EPI formula at Screening. One retest of the exclusionary eGFR value is allowed at Screening and Check-in at the discretion of the investigator.
- 14. Participant has abnormal liver function tests (transaminases greater

- than 2 \times the upper limit of normal [ULN]) or total bilirubin > 1.5 \times ULN. If the participant has documented Gilbert's Syndrome, participation is at the combined principal investigator and Sponsor's discretion after review of historical liver and bilirubin tests.
- 15. Participant has a positive serology test for HIV antibodies, hepatitis B surface antigen, or hepatitis C virus antibody at Screening.
- 16. Participant has a hemoglobin <11.0 g/dL, potassium <3.8 mg/dL, magnesium <1.8 mg/dL, or calcium <8.5 mg/dL at Screening or baseline. One retest of exclusionary hemoglobin, potassium, magnesium, and calcium is allowed at the discretion of the investigator.

- 17. Participant has a history of hypersensitivity to drugs with a clinically significant reaction or any clinically significant hypersensitivities.
- 18. Participant has a clinically significant allergy to band aids, adhesive dressing, ECG electrodes, or medical tape.
- 19. Participant has abnormal creatine phosphokinase test greater than 3 × ULN at Screening or baseline. One retest of exclusionary abnormal creatine phosphokinase tests is allowed at the discretion of the investigator.

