LQT-1213 or placebo matched to LQT-1213 will be administered at time 0, immediately after the 7.75-hour ECG extraction time point, and at 17 hours, though these time points may be adjusted based upon emerging data. Subjects will be discharged from the CRU on Day 9 or 10 (safety washout) in each period, if the QTcF is <460 ms and the increase from baseline is <40 ms. Day 10 evaluations will be performed if the subject is not discharged on Day 9. There will be a washout of at least 4 days (or at least 5 times the half-life) after the last dose of study drug. Subjects will return to the CRU on Day –2 and crossover to receive the alternate treatment in Period 2.

Approximately 7 days after the end of treatment in Period 2, the Follow-up Visit will be conducted remotely via telephone call.

Full PK sampling for dofetilide and LQT-1213 will be conducted on Days 4, 6, and 8 of each period. Continuous 12-lead 24-hour Holter data will be collected at the approximate 90-minute time point on Day –1 (corresponding to predose on Day 1) and stored, and on Day 1 starting 2 hours before dosing through Day 8. On each day, the Holter data card will be removed and a new one inserted 90 minutes before dosing. The ECGs will be extracted from the Holters on specific days and time points for core laboratory analysis, as detailed in the PK and PD time points table (Section 8.3, Appendix C).

Subjects will have an overnight fast on Days –1 through Day 8 and will remain fasted until immediately after the 6-hour ECG extraction, when a light meal will immediately be provided, followed by a meal immediately after the 9.5- and 12-hour ECG extraction time points.

Subjects will fast after the meals at 6 and 9.5 hours are completed, which must be within 20 minutes for these 2 time points. Subjects can eat at will after the 12-hour meal, a light meal will be provided, which must be completed to ensure the overnight fasting requirement is met (6-hour fast), (no food or fluid except water). Serum potassium and magnesium will be checked each day on Days –1, 1, and 2 and thereafter, beginning on Day 3, potassium and magnesium will be checked every other day. Potassium <3.8 mg/dL and magnesium <1.9 mg/dL will result in additional electrolyte supplementation. It is preferred, especially on Days 1, 4, 6, and 8, that this be done in the evening (after the 12-hour time point). Electrolyte supplementation is allowed at any time as long as it is >4 hours before dosing.

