3.1. Background

Congenital Long QT syndrome (LQTS) is a rare cardiac disorder most commonly caused by mutations in 1 of 3 genes that encode for ion channels involved in ventricular repolarization. Changes in the function of these ion channels result in ventricular action potential duration (APD) prolongation and prolongation of the QT interval corrected for heart rate (HR; QTc) interval, which can precipitate the ventricular arrhythmia Torsades de Pointes, which can lead to fainting, seizures, ventricular fibrillation, and sudden death. LQTS can also occur as the result of adverse effects of drugs and/or electrolyte abnormalities that inhibit the hERG (referred to as acquired LQTS).

Serum- and glucocorticoid-regulated kinase 1 (SGK-1) is a serine-threonine kinase that is under acute transcriptional control by several stimuli, including serum and glucocorticoids. SGK-1 is activated both by insulin and growth factor signaling. Baseline SGK-1 activity is low in cardiomyocytes but is upregulated in pathological states. SGK-1 plays a critical role in the regulation of the voltage-gated sodium channel Nav1.5 in cardiomyocytes by direct phosphorylation as well as regulation of interacting proteins (Bezzerides et al 2017). Activation of SGK-1 in the heart causes an increase in the late sodium current leading to prolongation of the APD, while genetic inhibition of the gene coding for SGK-1 reduces the increase in APD seen with both cardiac stressors and in inherited arrhythmia syndromes in animal models (Das et al 2012, Bapat et al 2021) and cell culture models (Bezzerides et al 2017), respectively. SGK-1 inhibition has been shown to reduce the APD in human-induced pluripotent stem cell-derived cardiomyocytes (hiPSC-CMs) from patients with several types of inherited arrhythmia syndromes such as LQT1 (potassium voltage-gated channel subfamily Q member 1 [KCNQ1] potassium channel locus; loss of function), LQT2 (potassium voltage-gated channel subfamily H member 2 [KCNH2] potassium channel locus; loss of function), and LQT3 (sodium voltage-gated channel alpha subunit 5 [SCN5A] sodium channel locus; gain of function) (Bezzerides et al 2017), as well as acquired LQTS in hiPSC-CMs treated with anemonia viridis toxin II or dofetilide and a guinea pig Langendorff model treated with dofetilide (Kim et al 2023).

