- 10. Abnormal renal function with an estimated glomerular filtration rate (eGFR) of <70 mL/min/1.73 m², with eGFR calculated by the Chronic Kidney Disease Epidemiology Collaboration [CKD-EPI] formula at Screening. One retest of the exclusionary eGFR value is allowed at the discretion of the investigator.
- 11. Subject has abnormal liver function tests (transaminases or total bilirubin) greater than 2.5 × the upper limit of normal at Screening or baseline. One retest of exclusionary abnormal liver function tests is allowed at the discretion of the investigator.
- 12. Subject has a positive serology test for HIV antibodies, hepatitis B surface antigen, or hepatitis C virus antibody at Screening.
- 13. Subject has a hemoglobin <11.0 g/dL, potassium <3.8 mg/dL, magnesium <1.9 mg/dL, or calcium <8.5 mg/dL at Screening or baseline. One retest of exclusionary hemoglobin, potassium, magnesium, and calcium is allowed at the discretion of the investigator. Electrolyte supplementation is allowed at any time as long as it is >4 hours before dosing.
- 14. Subject has a history of hypersensitivity to drugs with a clinically significant reaction or any clinically significant hypersensitivities.
- 15. Subject has an allergy to band aids, adhesive dressing, or medical tape.
- 16. Subject has a history within the past 2 months of strenuous exercise (eg, marathon running) and is unwilling to refrain from strenuous exercise from 7 days before Check-in and until the end of the study. Subject has abnormal creatine phosphokinase test greater than 3 × the upper limit of normal at Screening and baseline. One retest of exclusionary abnormal creatine phosphokinase tests is allowed at the discretion of the investigator.
- 17. Subject is unable to refrain from or anticipates the use of any drug, including prescription and nonprescription medications (with the exception of hormonal contraception), herbal preparations, or vitamin supplements beginning 14 days before the first dose and until the end of the study. After dosing, acetaminophen (up to 2 g per 24 hours) may be administered at the discretion of the investigator or designee.
 - a. Hepatic or renal clearance altering agents within 30 days before the first dose and until the end of the study.
 - b. Avoid vaccinations from Screening until the end of the study.

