- 9. At Screening and on Day –1, if the triplicate 12-lead ECG demonstrates any of the following: mean PR >250ms; QRS >110 ms, or QTcF >560 ms and <480 ms; bundle branch block or significant ST-T wave abnormalities or flat T waves that could interfere with QT analysis. Heart rate <45 bpm, unless receiving a beta-blocker in which case <40 bpm, or HR >95 bpm. If any of these exclusionary criteria are met, then a second set of triplicate ECGs may be acquired, and the mean values may be used. For participants on beta blockade, the PR interval may be higher than 250 ms with sponsor and investigator approval.
- 10. Atrial pacing rate set to \geq 80 bpm in those with atrial pacing.

- 11. Participant has a pacemaker or ICD that is actively used for ventricular pacing.
- 12. Known sensitivity to kinase inhibitors or clinically significant drug allergies to any of the components of LQT-1213.
- 13. Abnormal renal function with an eGFR of <60 mL/min/1.73 m², with eGFR calculated by the CKD-EPI formula at Screening. One retest of the exclusionary eGFR value is allowed at Screening and Check-in at the discretion of the investigator.
- 14. Participant has abnormal liver function tests (transaminases greater than 2 × the upper limit of normal [ULN] or total bilirubin > 1.5 × ULN. If the participant has documented Gilbert's Syndrome, participation is at the combined principal investigator and Sponsor's discretion after review of historical liver and bilirubin tests.
- 15. Participant has a positive serology test for HIV antibodies, hepatitis B surface antigen, or hepatitis C virus antibody at Screening.
- 16. Participant has a hemoglobin <11.0 g/dL, potassium <3.8 mg/dL, magnesium <1.8 mg/dL, or calcium <8.5 mg/dL at Screening or baseline. One retest of exclusionary hemoglobin, potassium, magnesium, and calcium is allowed at the discretion of the investigator.
- 17. Participant has a history of hypersensitivity to drugs with a clinically significant reaction or any clinically significant hypersensitivities.
- 18. Participant has a clinically significant allergy to band aids, adhesive dressing, ECG electrodes, or medical tape.
- 19. Participant has abnormal creatine phosphokinase test greater than 3 × the ULN at Screening or baseline. One retest of exclusionary abnormal creatine phosphokinase tests is allowed at the discretion of the investigator.

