5.4.5. Documentation of Concomitant Medications

Prior and concomitant medication information will be recorded beginning 30 days before study drug administration through Follow-up. Any therapy administered before informed consent is obtained will be recorded as a prior medication and medication ongoing at the time of signing the ICF or administered after informed consent will be recorded as a concomitant medication. Relevant information (ie, name of medication, dose, unit, frequency of administration, dates, and reasons for use) will be recorded in the source documents and in the eCRF. All changes in medication will be noted. If the reason for medication use meets the definition of an AE, the AE will be recorded on the appropriate page of the eCRF and in the source documents for that subject.

At the discretion of the principal investigator and/or medical monitor, additional potassium and/or magnesium can be administered to increase the electrolyte serum concentrations.

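### The potassium limit for exclusion and for mandatory supplementation is written as 3.8 mg/dL (0.97 mmol/L), so neither rule can operate as written

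*Protocol*

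**What the plan says.** The protocol uses a serum potassium limit for two purposes in each Part.

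**Exclusion.** Part 1 criterion 13 (Synopsis and Section 5.2.2.1) reads: "Subject has a hemoglobin <11.0 g/dL, potassium <3.8 mg/dL, magnesium <1.9 mg/dL, or calcium <8.5 mg/dL at Screening or baseline". Part 2 criterion 16 (Synopsis and Section 5.2.2.2) reads: "Participant has a hemoglobin <11.0 g/dL, potassium <3.8 mg/dL, magnesium <1.8 mg/dL, or calcium <8.5 mg/dL at Screening or baseline".

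**Mandatory supplementation.** For Part 1 (Synopsis study design, Section 5.1.1 and Table 5-1 footnote b): "Potassium <3.8 mg/dL and magnesium <1.9 mg/dL will result in additional electrolyte supplementation". For Part 2 (Synopsis study design and Section 5.1.2): "Potassium <3.8 mg/dL and magnesium <1.8 mg/dL will result in additional electrolyte supplementation".

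That makes four exclusion statements and five supplementation statements, all with potassium in mg/dL. No visible text gives the potassium limit in mmol/L or mEq/L. Section 5.4.5 separately provides, at the discretion of the principal investigator or medical monitor and with no numeric limit, that "additional potassium and/or magnesium can be administered to increase the electrolyte serum concentrations".

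**The concern.** A potassium limit of 3.8 is a natural number in mmol/L (equivalently mEq/L) but not in mg/dL. It stands next to magnesium and calcium limits that are correctly given in mg/dL, which suggests the unit was carried over from its neighbours.

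Potassium matters here because the study is about QT prolongation. Section 3.1 says: "LQTS can also occur as the result of adverse effects of drugs and/or electrolyte abnormalities". Part 1 gives healthy subjects dofetilide at the maximum US-labelled dose (Section 3.5). Part 2 enrolls patients with QTcF from 480 to 560 ms and checks potassium on every housed day, Days -1 and 1 to 5 (Section 5.1.2). If the limit cannot be reached, those checks feed a numeric rule that never acts. What is lost is the mandatory rule, not every route to correcting a low value.

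**Working it through.** The limit is a set threshold with no derivation in the documents, so there is no plan figure to reproduce. The check is a unit conversion.

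**Inputs from the protocol:** potassium 3.8 mg/dL (both Parts); magnesium 1.9 mg/dL (Part 1) and 1.8 mg/dL (Part 2); calcium 8.5 mg/dL (both Parts).

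**Constants:** molar mass K 39.0983, Mg 24.305, Ca 40.078 g/mol. Potassium is monovalent, so mmol/L equals mEq/L.

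**Formulas:** mmol/L = mg/dL × 10 / molar mass; mg/dL = mmol/L × molar mass / 10.

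1. Potassium limit as written: 3.8 × 10 / 39.0983 = 0.972 mmol/L.
2. The same number read in mmol/L: 3.8 × 39.0983 / 10 = 14.86 mg/dL. Ratio to the written limit: 14.86 / 3.8 = 3.91.
3. Can any plausible value fall below the written limit? The documents give no range for participants' potassium. I assume 2.0 to 5.0 mmol/L.

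| Potassium, mmol/L | mg/dL | Multiple of 3.8 mg/dL | Below the written limit? |
|---|---|---|---|
| 2.0 | 7.82 | 2.06 | No |
| 2.5 | 9.77 | 2.57 | No |
| 3.0 | 11.73 | 3.09 | No |
| 3.5 | 13.68 | 3.60 | No |
| 3.7 | 14.47 | 3.81 | No |
| 5.0 | 19.55 | 5.14 | No |

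4. Neighbouring limits: magnesium 1.8 × 10 / 24.305 = 0.741 mmol/L and 1.9 × 10 / 24.305 = 0.782 mmol/L; calcium 8.5 × 10 / 40.078 = 2.12 mmol/L. These are workable values, so the fault is confined to potassium.

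Over the whole assumed range the two potassium rules fire zero times if the text is applied literally. If 3.8 is read as mmol/L, the first five rows all qualify, including 3.7 mmol/L.

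**The case against.** The strongest reply concerns weight, not fact. No one running a cardiac safety unit is likely to apply a limit of 0.97 mmol/L; sites would read 3.8 as mmol/L or mEq/L, and the rule then works as intended. Other safeguards also remain:

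- The investigator must assess out-of-range laboratory values for clinical significance (Sections 5.4.3.3.1 and 5.4.3.3.2).
- Clinically relevant abnormal values may be treated (Sections 5.5.7.1 and 5.5.7.2).
- Potassium may be given at discretion (Section 5.4.5).
- The investigator may exclude anyone judged unsuitable (Part 1 criterion 25, Part 2 criterion 27).

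Timing also limits the benefit. Section 3.6.2 already cites Part 1 safety data, and SAP Section 6.4 describes a time interval added after the QTcF time course had been examined. The documents do not show whether anyone remains to be enrolled.

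All of this stands, and it limits the practical consequence. It does not make the text right. The safeguards are general or discretionary and do not replace a rule that obliges action below a stated number. Part 2 screening may be remote and its testing may use a local laboratory (Sections 5.1.2 and 5.4.3.3.2), so an eligibility limit should not depend on each reader silently replacing the unit. A text-extraction fault is not a credible explanation, given the identical wording in the Synopsis, the body and a table footnote.

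The supplementation sentence also joins potassium and magnesium with a conjunction that could be read as requiring both to be low. That is a separate drafting question, and this finding does not depend on it.

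**Conclusion.** The concern holds. All nine visible potassium limits carry a unit that places the threshold at 0.97 mmol/L, a factor of 3.9 below the same number in mmol/L. As written, neither the potassium exclusion nor the mandatory potassium trigger can fire for any value in the assumed range of 2.0 to 5.0 mmol/L. That range, and mmol/L as the intended unit, are assumptions; the conversion is not.

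The practical effect runs from nil, if sites read mmol/L or mEq/L, which is probable, to complete loss of both numeric rules under a literal reading. No harm and no effect on a study estimate is shown. The point should be fixed because the error is certain, it sits in an eligibility criterion and a safety rule, and correcting it is cheap.

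**What to change.** Correct the potassium unit in the four exclusion statements and five supplementation statements listed above, using the unit the study laboratory reports: most likely 3.8 mmol/L (the same as 3.8 mEq/L), or 14.9 mg/dL. The medical lead should confirm the intended value. Leave the magnesium and calcium limits unchanged. Check the electrolyte footnote in the Appendix A schedule of events, which is not visible here, for the same unit.

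For participants already screened or treated, record in a note to file which unit was applied. For them this is a documentation step only.

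The cost is one text correction repeated in nine visible places, the note to file, and submission of the amendment to the IRB as Section 7.2.1 requires. No new visit, sample or procedure is needed.
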